## **11.1.** Adverse Event Definitions

	All cases judged by either the reporting medically qualified professional or the Sponsor as having a reasonable suspected causal relationship to the trial medication qualify as adverse reactions.		
Serious Adverse Event (SAE)	
 
A serious adverse event is any untoward medical occurrence that:
 
results in death
 
is life-threatening
 
requires inpatient hospitalisation or prolongation of existing hospitalisation
 
results in persistent or significant disability/incapacity
 
consists of a congenital anomaly or birth defect*.
 
Other 'important medical events' may also be considered a serious adverse event when, based upon appropriate medical judgement, the event may jeopardise the participant and may require medical or surgical intervention to prevent one of the outcomes listed above.
 
		
	NOTE: The term "life-threatening" in the definition of "serious" refers to an event in which the participant was at risk of death at the time of the event; it does not refer to an event which hypothetically might have caused death if it were more severe.		
Serious Adverse Reaction (SAR)	An adverse event that is both serious and, in the opinion of the reporting Investigator, believed with reasonable probability to be due to one of the trial treatments, based on the information provided.		
Suspected Unexpected Serious Adverse Reaction (SUSAR)	
 
A serious adverse reaction, the nature and severity of which is not consistent with the Reference Safety Information for the medicinal product in question set out:
 
in the case of a product with a marketing authorisation, in the approved summary of product characteristics (SmPC) for that product
 
in the case of any other investigational medicinal product, in the approved investigator's brochure (IB) relating to the trial in question.
 
		

NB: to avoid confusion or misunderstanding of the difference between the terms "serious" and "severe", the following note of clarification is provided: "Severe" is often used to describe intensity of a specific event, which may be of relatively minor medical significance. "Seriousness" is the regulatory definition supplied above.

## **11.2.** Assessment results outside of normal parameters as AEs and SAEs

Only events considered related to the AI treatment in the pre-surgical window and considered serious are recorded as SAEs. This includes any assessment results outside of normal parameters.

EndoNET\_Protocol\_V4.0\_21Aug2024

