# **11. SAFETY REPORTING (Main Trial)**

The trial will be run in accordance with OCTRU's Standard Operating Procedures (SOPs) and operational policies, which all adhere to applicable UK regulatory requirements.

An independent Data and Safety Monitoring Committee (DSMC) and Trial Steering Committee (TSC) will be appointed. The DSMC will monitor data arising from the trial, review confidential interim reports of accumulating data, and recommend whether there are any ethical or safety reasons why the trial should not continue. The TSC will monitor the trial's progress and will provide independent advice. Both committees will comprise independent clinicians, statisticians, health service researchers and patient representatives.

Adverse Event (AE)	Any untoward medical occurrence in a participant to whom a medicinal product has been administered, including occurrences which are not necessarily caused by or related to that product.
Adverse Reaction (AR)	An untoward and unintended response in a participant to an investigational medicinal product which is related to any dose administered to that participant. The phrase "response to an investigational medicinal product" means that a causal relationship between a trial medication and an AE is at least a reasonable possibility, i.e. the relationship cannot be ruled out.

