## 11.6. Assessment of Causality

The relationship of each serious adverse event to the trial medication must be determined by a medically qualified individual according to the following definitions:

	Attribution (Causality)	Description	
Non-related	Unrelated	The AE is clearly NOT related to the intervention	
	Unlikely	The AE is doubtfully related to the intervention	
Related	Possibly	The AE may be related to the intervention	
	Probably	The AE is likely related to the intervention	
	Definitely	The AE is clearly related to the intervention	

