## **11.9.** Reporting Adverse Events and SAEs including reporting period

All side effects collected as outcomes in the CRF that also meet the definition of serious will need to be reported as an SAE during the trial's safety reporting window. All other SAEs considered related to the AI treatment should also be reported on an SAE form. Reporting must be within 24 hours of the site being aware of the SAE. Once a SAE is entered in the database, this automatically triggers a notification to the CTU.

The following information will be reported on the SAE form: relevant brief medical history, description of event (i.e. diagnosis term), date of onset and end date, severity, assessment of relatedness to trial medication, or drug–to drug interaction if participant is taking concomitant drugs; reason for seriousness, and action/s taken to deal with the event. SAEs will be closed following resolution. Follow-up information should be provided as necessary.

In the event that the clinical database is not available for reporting of SAEs within 24 hours, sites must complete a paper SAE Form and email it to the trial inbox email account: [contact].

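### The protocol's safety sections conflict on which pre-surgical serious events are reported as SAEs, and the SAR definition is narrower than both the AR definition and the 11.6 causality scale

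*Protocol*

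**What the plan says.** All references are to the protocol.

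- **SAE definition (11.1).** "A serious adverse event is any untoward medical occurrence that" meets one of the seriousness criteria, death among them. Causality is not a condition.
- **Recording rule (11.2).** "Only events considered related to the AI treatment in the pre-surgical window and considered serious are recorded as SAEs". The schedule of procedures in 9.2 likewise makes AI-related SAEs reportable until surgery. The second sentence of 11.9 asks for all other SAEs only where they are considered related.
- **Listed side effects (11.5 and 11.9, first sentence).** 11.5 lists frequent AI side effects, including vomiting, anorexia and urinary tract infection. It requires them as SAEs when they are serious and fall in the reporting window. 11.9 opens in the same way: "All side effects collected as outcomes in the CRF that also meet the definition of serious will need to be reported as an SAE" during that window. Neither sentence adds a relatedness test.
- **Causality (11.6).** "The relationship of each serious adverse event to the trial medication must be determined by a medically qualified individual". There are five grades: Unrelated and Unlikely count as non-related; Possibly, Probably and Definitely count as related.
- **Adverse reaction (AR; Section 11, continued in 11.1).** The causal link is one that "is at least a reasonable possibility, i.e. the relationship cannot be ruled out". On who decides: "All cases judged by either the reporting medically qualified professional or the Sponsor as having a reasonable suspected causal relationship to the trial medication" qualify.
- **Serious adverse reaction (SAR; 11.1).** An event that is serious and, "in the opinion of the reporting Investigator, believed with reasonable probability to be due to one of the trial treatments". A SUSAR is a SAR not consistent with the reference safety information. 11.12.1 sets 7 calendar days for reporting fatal or life-threatening SUSARs and 15 for the rest.

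**The concern.** A site cannot follow all of these at once. Two sites faced with the same event could act differently, each with the protocol on its side, and the SAE listing would then depend on which section a site happened to use.

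The second problem lies further down the chain. Expedited reporting starts from SUSARs, and SUSARs start from SARs. If the SAR threshold is higher than the AR threshold, and is held by one judge instead of two, some serious events that the protocol itself calls related can fall out before expectedness is assessed.

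What is at stake is which events reach the CTU, the regulator and the safety listings. The reporting window runs to surgery: 6 months (+/- 1 month) in the NET arm against a target of 2-4 weeks (up to 8 weeks) in control. Any inconsistency therefore acts for longer in the NET arm.

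**Working it through.** No arithmetic applies. The check takes four kinds of pre-surgical serious event and runs each through the rules.

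| Event | Rules that bring it in | Rules that leave it out |
|---|---|---|
| A. On the 11.5 list, judged Unrelated or Unlikely (e.g. admission for a urinary tract infection) | SAE by 11.1; reportable under 11.5 and 11.9 first sentence | 11.2; schedule |
| B. Not on the list, judged Unrelated or Unlikely | SAE by 11.1; 11.6 asks for a grade | 11.2; 11.9 second sentence; schedule |
| C. Unexpected, graded Possibly | SAE by 11.1 and 11.2; related by 11.6; meets the AR threshold | SAR definition, if the Investigator does not hold it reasonably probable |
| D. On the list, judged Unlikely at site, but the Sponsor sees a reasonable suspicion | AR by 11.1, through the Sponsor | SAR definition, which names the Investigator only |

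**A** is a direct contradiction: the same event is to be reported and not to be reported.

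**B** shows two gaps. First, if only related events are recorded, the Unrelated and Unlikely grades have no use outside the 11.5 list. Second, 11.10 gives the CTU an initial check and a Nominated Person review of SAEs that have been notified. A type B event is never notified, so the Sponsor has nothing on which to form the alternative judgement that 11.1 allows. (11.2 does not say who does the considering. That it is the site is inferred from 11.1, 11.6 and 11.9.)

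**C** turns on the two thresholds. Possibly counts as related in 11.6 and fits the possibility wording of the AR definition. The SAR definition asks for probability. The event can then be a serious AR without being a SAR; 11.11 assesses the expectedness of SARs, and 11.12.1 acts on SUSARs. Read literally, the expedited report is not triggered.

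**D** shows that even where the CTU has the form and disagrees with the site, the Sponsor's view makes the event an AR but not a SAR.

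Is the related-only filter justified elsewhere? 11.8 explains why the window ends at surgery, because the AI is then no longer an IMP. It does not explain why unrelated events inside the window are left out.

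**The case against.** **The filter is deliberate.** It appears in 11.2, in the second sentence of 11.9 and in the schedule, and the trial is Type A, where lighter reporting is to be expected. This stands: a related-only rule may be what the sponsor wants, and half of 11.9 agrees with 11.2. It does not reconcile 11.2 with 11.5, 11.6 or the first sentence of 11.9.

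**The term side effect may already imply relatedness.** 11.5 is headed as side effects in relation to the IMP. On that reading type A events drop out and the conflict with 11.5 softens. But the non-related grades in 11.6 then serve no recorded SAE, unless the person who first considers the event differs from the one who grades it, which the protocol does not say. If instead listed events are reported whatever their cause, those grades have a use but 11.2 is contradicted. Each reading leaves a conflict.

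**11.6 already treats Possibly as related.** True, and in practice a CTU may process such events as SARs. The SAR definition still says otherwise.

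Some stronger readings are tempting and are not supported:

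- A reader might infer that 11.1 requires a Sponsor causality review which 11.2 removes. 11.1 permits the Sponsor's judgement as an alternative; it does not mandate a second look.
- A reader might infer that pre-surgical deaths go unreported. Those judged unrelated are not reported as SAEs, but overall survival is an outcome at 15 months (6.2), admissions and deaths are still captured after withdrawal from follow-up unless the participant objects (9.16), and the DSMC sees accrued data or summaries by arm (14.1.3).
- A reader might infer a long delay before a death is noticed. The NET arm has an ultrasound and clinical assessment at 5 months and surgery at about 6 months, so a wait until month 15 is not established.
- Open-label treatment is not the cause. Both arms take an AI before surgery, and none of these conflicts depends on blinding.

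**Conclusion.** The concern holds as two internal contradictions: one about which serious events are recorded as SAEs, the other about the threshold for a SAR and whose opinion decides it. The first affects serious listed events judged unrelated. It also leaves the Sponsor limb of 11.1 without effect for unlisted events judged unrelated. The second affects serious unexpected events graded Possibly, and events where the Sponsor but not the Investigator suspects the drug; it bears on 7- and 15-day reporting.

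The size can be stated only as classes of event. The protocol gives no rate of serious events, and a count would rest entirely on an assumed one. The primary outcome and its analysis are not affected. The conclusion assumes that sites apply the text as written and that the considering in 11.2 is done at site. The matter should be put right because the remedy is cheap and changes which events reach SUSAR reporting.

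**What to change.** 1. Reconcile 11.1, 11.2, 11.5, 11.6, 11.9 and the schedule of procedures into one reporting rule.
2. State in 11.2 whether serious events on the 11.5 list are reported regardless of attribution. If so, write the exception into 11.2 and the schedule. If not, add the relatedness condition to 11.5 and the first sentence of 11.9, and say when the non-related grades in 11.6 apply.
3. Align the SAR definition with the AR definition and 11.6: at least a reasonable possibility, in the opinion of the Investigator or the Sponsor.
4. Decide, and state explicitly, whether fatal or life-threatening pre-surgical events judged unrelated are sent to the CTU and listed by arm for the DSMC. Either answer can be defended. Making the Sponsor's suspicion a trigger for site reporting would not help, because the Sponsor cannot judge an event it has not received. If the filter stays, say that the Sponsor limb covers notified events only.

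The cost is a protocol amendment and, depending on items 2 and 4, a few more SAE forms. SAE capture may then differ before and after the amendment, so the date of change should be shown in the safety listings.

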## 9.14.2. Sample handling for trial purposes

Participants in both arms will receive, as standard of care, a breast core (or percutaneous image guided) biopsy for diagnosis. A further sample should be available from the surplus tissue at surgery. The trial will request tissue surplus to diagnostic requirements from biopsy blocks at baseline and the resected surgical specimen. In the NET arm, a further research core biopsy of the tumour will be taken for the trial, at the same time as the marker/clip is inserted after 2-4 weeks. All samples collected for the trial will be labelled with a unique trial ID number. Sample cores collected will vary in size, but usually those taken from diagnostic samples and from the 2-4 week clip insertion (NET arm only) will be the equivalent to a few grains of rice.

The research core biopsy samples should be formalin fixed and processed as per the latest UK guidelines (https://www.rcpath.org/uploads/assets/4b16f19c-f7bd-456c-b212f557f8040f66/G150-Non-opreporting-breast-cancer-screening.pdf). H&E examination should be undertaken to confirm the presence of breast carcinoma; full histological review and report for this sample is not required.

The core biopsy specimen blocks (both from diagnostic and research cores) and representative block(s) from the surgical specimen will be collated by the Faculty of Medicine Tissue Bank at the University of Southampton (HTA Licence No: 12009) as part of this study. Sites are responsible for ensuring that samples are sent securely to the Tissue Bank with the appropriate tracking documentation in place. Samples should be packaged safely and appropriately under the right environmental conditions accompanied with a signed and dated consent form. The Tissue Bank is responsible for storing the samples under the appropriate environmental conditions and for tracking the samples with the relevant documentation.

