## **10.3 Other Interventions (Main Trial)**

There are no additional interventions in the trial.

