# **11.3.** Events exempt from reporting as AE/SAEs

Hospitalisation for a pre-existing condition, including elective procedures planned prior to study entry, which has not worsened, does not constitute a reportable serious adverse event; e.g., hospitalisation for procedures and treatments specified within the protocol, and standard supportive care for the disease under study are not reportable SAEs, and do not require SAE reporting.

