## **11.4.** Reporting complications in relation to surgery

Any complications related directly to breast surgery and not considered related to AI treatment (example: prolonged hospitalisation, infection etc.) will not be part of the safety reporting but will be collected in the relevant trial CRF. These will be assessed using the Clavien-Dindo Classification of surgical complications.

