## 11.5. Reporting side effects in relation to IMP treatment

Side effects frequently experienced by patients undergoing AI therapy for breast cancer are collected as outcomes in the trial's CRF for the duration of patient participation in the trial (15-months for both arms) and include the following:

- Vasomotor including hot flashes/flushes and night sweats/hyperhidrosis
- Musculoskeletal including myalgia and arthralgia/joint pain;
- Central nervous system including nausea, vomiting, and fatigue;
- Urogenital including vaginal haemorrhage/bleeding, vaginal dryness and urinary tract infection;
- Gastrointestinal including anorexia;
- Other including alopecia.

Generally, these are mainly mild or moderate in nature, and most are associated with oestrogen deprivation.

The above events must also be reported as SAEs if they meet the definition of serious and occur during the trial's defined safety reporting window.

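### Serious complications of the NET-arm 2-4 week research biopsy, or of the trial-required clip, have no stated route as SAEs or as attributed harm

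*Protocol*

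**What the plan says.** **The procedure.** Section 9.14.2: "In the NET arm, a further research core biopsy of the tumour will be taken for the trial", at the visit when the clip is placed. Section 9.9.1 makes the 2-4 week ultrasound a requirement of the NET arm, for placing the clip and taking cores for Ki67. Section 9.2 counts it among the NET arm's additional visits. Section 9.14.2 adds that the biomarker assessment is done centrally in batches and is not needed for real-time decisions. Section 10.3 nevertheless says: "There are no additional interventions in the trial".

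**The safety rules.**
- Section 11.1 defines seriousness broadly: "A serious adverse event is any untoward medical occurrence that" meets one of the listed criteria, which include inpatient hospitalisation.
- Section 11.2 narrows what is recorded: "Only events considered related to the AI treatment in the pre-surgical window and considered serious are recorded as SAEs".
- Section 11.9 requires SAE reports for the CRF-listed side effects that are serious, and then: "All other SAEs considered related to the AI treatment should also be reported on an SAE form".
- Section 11.5 describes that list: "Side effects frequently experienced by patients undergoing AI therapy for breast cancer are collected as outcomes in the trial's CRF". The entries are vasomotor, musculoskeletal, central nervous system, urogenital, gastrointestinal and other AI effects.
- Section 11.4 moves one class of event out of safety reporting and onto a CRF: "Any complications related directly to breast surgery and not considered related to AI treatment".
- Section 11.8 sets the window from consent to surgery.

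**The concern.** The trial adds an invasive procedure for research in one arm. The safety section then admits only events attributed to the drug, and it gives a substitute route only to surgical complications. A serious complication of the biopsy or clip appears to fall between the two.

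At stake is oversight of harm from a procedure that participants undergo for the trial. The Trial Management Group is to watch for trends in SAEs, and the Data and Safety Monitoring Committee is to assess the safety of the interventions. Neither has a stated route by which such an event would reach them identified as a complication of the procedure. The definition in 11.1 and the recording rule in 11.2 also disagree about the same event, so sites could handle it differently.

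**Working it through.** **1. Follow one event through the text.** Take a NET participant admitted with a biopsy-site infection or bleed shortly after the 2-4 week visit, judged unrelated to the AI.

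| Section | Question | Result |
|---|---|---|
| 11.1 | Does it meet the SAE definition? | Yes: untoward occurrence needing inpatient admission |
| 11.8 | Is it inside the safety window? | Yes: after consent, before surgery at 6 months (+/- 1 month) |
| 11.2 | Is it recorded as an SAE? | No: not related to the AI |
| 11.5 and 11.9 | Is it a listed side effect, reportable if serious? | No: no biopsy-site or clip event is listed |
| 11.9 | Is it reportable as another SAE? | No: AI-related only |
| 11.4 | Is it collected on the surgical complications CRF? | Not as stated: limited to breast surgery |
| 6.2, outcome 6 | Is it within the harm outcome? | Not as stated: post-surgical complications and AI side effects |

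Sections 11.2 and 11.9 settle this by an express rule, not by silence. Section 11.3 is not needed for the result and is left out of the chain (see the objection).

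**2. How many participants are exposed.** Inputs from section 12.3: BCS 55% versus 65%, two-sided 5%, power 80% or 90%, 5% cross-over and attrition, 1:1.

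n per arm = [1.96 × √(2 × 0.60 × 0.40) + z_power × √(0.55 × 0.45 + 0.65 × 0.35)]² / 0.10²

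- 80% power (z = 0.8416): (1.3579 + 0.5800)² / 0.01 = 375.6, so 376 per arm and 752 in total; 752 / 0.95 = 791.6, so 792. Stated: 792.
- 90% power (z = 1.2816): (1.3579 + 0.8833)² / 0.01 = 502.3, so 503 per arm and 1006 in total; 1006 / 0.95 = 1058.9, so 1059. Stated: 1060.

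Both totals reproduce (the second to within rounding). They allocate 792 / 2 = 396 to 1060 / 2 = 530 women to NET. These are upper figures for exposure, since early surgery or withdrawal would remove some women before the biopsy.

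**3. Expected serious events.** The documents give no complication rate, so the rate p is an assumption. Expected events = N × p; chance of at least one = 1 − (1 − p)^N.

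| Assumed serious rate | N = 396 | N = 530 |
|---|---|---|
| 0.1% | 0.4 events; 33% | 0.5 events; 41% |
| 0.5% | 2.0 events; 86% | 2.65 events; 93% |
| 1% | 4.0 events; 98% | 5.3 events; 99.5% |

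The count is small across the range. At the lowest rate, no event at all is the more likely result.

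**The case against.** Several stronger readings are tempting, and the documents do not support them.

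- **That such harm is never reported or counted, or that the committees cannot see it.** Section 13.3.1 lets sites check hospital records for admissions. Section 9.16 provides for continued capture of admissions and deaths after withdrawal from follow-up. The section 12.8 questionnaire asks about resource use, including complications. Deaths count in overall survival. The DSMC sees accrued data or summaries by arm. What is missing is attribution to the procedure and an SAE route.
- **That section 11.3 exempts these complications.** It exempts "hospitalisation for procedures and treatments specified within the protocol". Its natural reading is the planned admission, not harm arising from the procedure.
- **That causality is judged solely against the drug.** The lead-in to section 11.6 names the trial medication, but its five attribution categories refer to the intervention. That wording is ambiguous, not an exclusion.
- **That both procedures are confined to NET.** The research biopsy is. Table 1 in section 5.2 says a control-arm clip may be needed, and section 5.4 gives the clip a clinical purpose.
- **That NET is made to look safer.** The biopsy is a research sample and not part of NET as a treatment. Merging its complications into outcome 6 would charge NET with harm from the research.

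Two general defences remain. First, this is a Type A, risk-adapted trial of established drugs. That classification concerns the risk of the medicines, and the reason given in section 11.8 covers only AI use after surgery; neither justifies excluding harm from a research procedure. Second, a CRF field may exist that the protocol does not describe: outcome 6 has a 2-4 week timepoint, and the schedule table's row labels are not legible in the text available. That possibility stands for CRF collection, but it would not alter the SAE rule in 11.2 and 11.9.

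**Conclusion.** The point holds in limited form. A serious complication of the research biopsy or trial-required clip, judged unrelated to the AI, meets the protocol's own SAE definition inside its own window. It is nevertheless excluded from SAE recording, and no other route is stated that would collect it as harm from the procedure. Section 10.3 contradicts sections 9.2, 9.9.1 and 9.14.2.

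The size is about 0.4 to 5.3 serious events over the trial. This rests on an assumed rate of 0.1-1% and on every woman allocated to NET having the procedure. The case for acting is that the biopsy is done for research and the repair is cheap, not that results would shift. The safety text should be corrected.

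**What to change.** - **11.2, 11.6 and 11.9:** extend recording, causality assessment and reporting to serious events related to the AI or to a trial-specific procedure, named as the 2-4 week research biopsy or clip insertion. This also reconciles these sections with 11.1.
- **2-4 week CRF:** record biopsy and clip complications, serious or not, if no field already does so. Report them to the DSMC and in the results as a separate item, not merged into outcome 6.
- **10.3:** list the biopsy and clip.

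Cost: an amendment to the safety text, one or two CRF fields at an existing visit, and a few more SAE reports.
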